9.5 Personal Data breaches

Personal data breaches will be immediately reported to the UCL Information Security Group (ISG) and the UCL Data Protection Officer [[contact]], and to the Sponsor via the [UCL JRO research incident reporting form](#) (as per form and guidance: <https://www.ucl.ac.uk/legal-services/guidance/reporting-loss-personal-data>). The following information will be provided: full details as to the nature of the breach, an indication as to the volume of material involved, and the sensitivity of the breach (and any timeframes that apply). Sites will additionally follow their Trust incident reporting mechanisms, and will document this within their TMF/ISFs.

10. STATISTICAL CONSIDERATIONS

10.1 Primary outcome

Outcome Measure: Average number of aerosol droplets per minute per clinical encounter as measured by an air particle counter (APC) installed next to the clinician and at up to 4 other fixed locations in the room or ward bay.

10.2 Secondary outcome(s)

Secondary Objective: Mixed methods evaluation of staff experiences of using the tool and the mitigation approaches that are recommended (based on analysis of acceptability by staff and

feasibility of implementation), as well as questionnaires for patients and the cost-efficiency evaluation.

Outcome Measures:

1. Normalisation Measure Development Questionnaire (NoMAD)
2. Ethnographic observations using formal and informal interviews to explore hospital staffs' views on the importance of AISaT, usability and management of the AISaT software and challenges to fidelity in implementation, and how team members can work together effectively to support implementation
3. An estimation of the cost efficiency of AISaT

10.3 Sample size calculation

Participants: 3 consulting rooms or 3 AGP rooms in each hub hospital. 54 clinicians who regularly use these rooms (27 per hospital approximately) will be invited to take part, each for 3 consecutive weeks.

A 3-period, 3-treatment cross-over design will be used to test whether there is a difference in the 3 means. The comparison will be made using a Geisser-Greenhouse corrected F-test with a Type I error rate (α) of 0.05. The group means under the null hypothesis are assumed to be equal. The standard deviation across subjects at the same period is assumed to be 1 (and the means are expressed, see below, as a fraction of the standard deviation, which allows us to calculate a sample size using the Cohen's D approach). The assumed pattern of the covariance matrix is 'all correlations equal' (compound symmetry) with a correlation of 0.5 between adjacent time point measurements. To detect group means of '0 0.25 0.5' with 90% power, the needed number of clinicians is 53 (each measured 3 times). Given that there are six possible sequence combinations of the 3 treatments, the sample size is increased to the closest multiplicator of 6, which is 54. The sample size was computed using PASS 2024, version 24.0.2.

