3. OBJECTIVES AND OUTCOME MEASURES/ENDPOINTS

3.1 Primary Objective

Primary Objective: To determine in hospital outpatient consulting rooms, aerosol generating procedure rooms and wards, when using mitigations for airborne disease transmission according to recommendations of the AISaT software tool, the reduction in the relative number of airborne aerosol droplets per standard time period which will be breathed by clinicians compared to when no mitigations are used or when mitigations are used as decided by the clinician using the relevant space.

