10.4 Planned recruitment rate

Two hospitals are recruiting to this study. The crucial participants to recruit for the first pilot and trial stage 1 is 27 clinicians in each hospital who perform outpatient consultations or aerosol generating procedures (AGPs). Of these, 12 will take part in both the pilot and the stage 1 trial. UCLH has a clinical staff of many thousands and sees 1,800,000 out-patients each year. This equates to around 200,000 separate clinic sessions in multiple clinical areas and there are many dozens of clinical consulting and AGP rooms throughout the estate. The Lister Hospital also has over 2,000 clinical staff and sees 800,000 outpatients each year (around 90,000 separate clinic sessions) and also has multiple clinical areas available. The PI at each site will engage local clinical colleagues, managers and clinical directors to support the work and clinicians who are expected to be in clinic for 3 weeks consecutively will be targeted for recruitment. We expect a dropout rate of around 5% as clinicians must give a minimum of 6 weeks' notice to cancel a clinic, so it is expected that the vast majority of clinicians who agree to take part will attend the relevant clinic sessions.

Recruitment is anticipated to be 10 clinicians per month for stage 1 and its pilot. For stage 2 (and its pilot), 54 clinicians will again be needed. Some of these may be the same ones who participated in stage 1. Recruitment is again anticipated to be 10 clinicians per month. The PI at the Lister Hospital and the CI, who works at UCLH, are both active clinicians who work in outpatients and AGP rooms. This should make recruitment of their clinical colleagues relatively straightforward. The dropout rate is again around 5% as described above.

Of patients attending these clinics and AGP sessions, almost 100% will be eligible and all of these will be invited to take part in the studies (we will not recruit in paediatric, obstetric or psychiatric clinics). Recruitment of patients is therefore likely to be around 300 with approximately 150 accompanying persons per month in both trial stages 1 and 2. Patients will either accept and enrol in the trial, or will not. If they accept and enrol, we do not expect drop-outs. If there were to be, this should have no major impact on the trial endpoints as we will be able to control for this in the data analysis phase. For a 4-hour clinical session, we expect to have 3 hours of analysable data approximately.

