For trial stage 3 and its pilot, a total of 12 patient bays is required, 6 at each hospital and each will participate for 3 days. There is no formal sample size calculation for stage 3, as it requires inputs that we do not possess at the moment, including the correlation between the measurements within a bay, as well as the correlation over time. The design is a cluster randomised cross-over control trial. Given that there are 6 possible sequences of the 3 configurations, we chose 12 bays so that there are 2 bays per sequence.

Decisions about wards will be driven by senior clinical management. In wards, if patients accept the study, they will be in the bay until they are discharged, so no drop out is expected. Recruitment of other hospital staff to join the implementation science elements of the study is expected to be around 8-10 per month across the two sites for the duration of the study.

Loss to follow up is not considered to be relevant as participation is only for a very short period of time.

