10.8 Primary outcome analysis

Data analysis will be linear mixed modelling of the paired data (3 conditions for each clinician) controlling for confounding factors which may include: number of people in the room, baseline ventilation, room size, room shape, temperature, humidity and various other factors (see full list of suggested confounding factors in study design section). The power of the trial based on the UK sites alone is 90%.

Data analysis relies on properly functioning aerosol generators and particle counters. In stages 1 and 2, we will check each piece of machinery is working properly before the beginning of the clinical session. Where we do not manage to collect data for at least 2 hours in a clinical session, that session will be withdrawn from the study and repeated in its entirety. We expect this to happen in less than 5% of clinic sessions. For stage 3, a minimum of 6 hours data per day is required otherwise that day's randomisation will need to be rerun.

There are no plans for predefined subgroup analyses in stages 1 and 2. For stage 3, subgroup analyses will include daytime (8 am to 8pm) versus nighttime (8 pm to 8 am).

We will employ the intention-to-treat (ITT) analysis method to ensure the integrity and validity of our RCTs.

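### The 90% power in sections 10.3 and 10.8 is for an omnibus F-test; on the same inputs at least one of the two AISaT comparisons in the primary objective has only about 44%

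*Protocol*

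**What the plan says.** The primary objective (Protocol 3.1, and the study summary) is the reduction in droplets under AISaT "compared to when no mitigations are used or when mitigations are used as decided by the clinician using the relevant space". That names two comparators.

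Section 10.3 frames the sizing question differently: "A 3-period, 3-treatment cross-over design will be used to test whether there is a difference in the 3 means". The test is an omnibus one: "The comparison will be made using a Geisser-Greenhouse corrected F-test with a Type I error rate (α) of 0.05". On scale, "The standard deviation across subjects at the same period is assumed to be 1", with compound symmetry and a correlation of 0.5. The result is: "To detect group means of '0 0.25 0.5' with 90% power, the needed number of clinicians is 53 (each measured 3 times"), raised to 54 so that it divides by the six sequences.

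Section 10.8 plans a linear mixed model of the three conditions and adds: "The power of the trial based on the UK sites alone is 90" per cent. It does not say which test or which stages this covers. For the wards, section 10.4 says: "There is no formal sample size calculation for stage 3".

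The protocol does not say which configuration carries which of the three planning means, and it gives no power for either AISaT comparison.

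**The concern.** An omnibus F-test asks whether the three means are all equal. Rejecting it does not show that AISaT differs from either comparator. It can reject because devices of any kind beat no devices, which says nothing about whether the software places them better than a clinician would.

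The comparison with clinician placement is the one that separates the tool from the hardware: section 2 stresses that device location drives performance, and section 6.1 describes AISaT as recommending devices and their placement. A reader of section 10.8 would take 90% to cover that comparison. A null result against clinician placement could then be read as well-powered evidence of no benefit, and a significant F-test as evidence for AISaT. The stated figure supports neither reading.

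**Working it through.** **Inputs, all from Protocol 10.3:** means 0, 0.25 and 0.5; SD 1; correlation 0.5 with compound symmetry; alpha 0.05; 53 clinicians, raised to 54. Pairwise tests are taken as two-sided at 5%.

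**Step 1: reproduce the plan's figure.** Under compound symmetry the Geisser-Greenhouse epsilon is 1, so the test is a repeated-measures F with 2 and 2(n − 1) degrees of freedom.

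- Sum of squared deviations of the means: 0.25² + 0² + 0.25² = 0.125
- Noncentrality: λ = n × 0.125 / (1 − 0.5) = 0.25n

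| n | λ | Omnibus power |
|---|---|---|
| 52 | 13.00 | 89.9% |
| 53 | 13.25 | 90.5% |
| 54 | 13.50 | 91.1% |

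So 53 is the smallest number that reaches 90%. The sample size arithmetic is right.

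**Step 2: power for a single pair.** The SD of a within-clinician difference is √(2 × (1 − 0.5)) = 1. For a paired t-test the noncentrality is δ√n, with n − 1 degrees of freedom. At n = 54, √54 = 7.348.

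| Difference δ | Noncentrality | Power, alpha 0.05 | Power, alpha 0.025 |
|---|---|---|---|
| 0.25 SD | 1.837 | 43.8% | 32.7% |
| 0.5 SD | 3.674 | 95.0% | 91.1% |

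Using pooled cross-over error degrees of freedom, or a normal approximation, moves the 0.25 SD figure only to 44.5% or 45.1%. The difference detectable with 90% power at n = 54 is 0.449 SD. For scale, 90% power at 0.25 SD would need 171 clinicians.

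**Step 3: does the missing mapping matter?** AISaT can sit in three positions among the planning means.

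- At either end (0 or 0.5): its two gaps are 0.25 and 0.5.
- In the middle (0.25): both gaps are 0.25.

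In every case at least one AISaT contrast is 0.25 SD. If AISaT and no mitigation are the extremes, it is the contrast with clinician placement.

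**Step 4: what the omnibus test does when AISaT adds nothing to clinician placement.** Take no mitigation at one value and the other two configurations both 0.5 SD from it. The means are 0, 0.5, 0.5 with average 1/3.

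- Sum of squares: (1/3)² + 2 × (1/6)² = 1/6
- λ = 54 × (1/6) / 0.5 = 18
- Power: 97.1%

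**Step 5: joint behaviour, by simulation at n = 54 under the planning means with AISaT at one extreme.** Both AISaT contrasts are significant in about 43% of trials. The omnibus test is significant while the 0.25 SD contrast is not in about 48%.

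**The case against.** **The F-test is only a sizing device.** It appears in section 10.3 and nowhere else. Section 10.8 plans a mixed model, which can estimate each contrast, and the contrasts and their multiplicity control may be in a statistical analysis plan that is not shown. This stands in part: a reader might infer that the omnibus test is the trial's success criterion, and the protocol does not say so. But an analysis plan cannot change what the protocol's 90% refers to.

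**Powering an omnibus test is a recognised design.** With exactly three treatments, an omnibus gate followed by unadjusted pairwise tests controls familywise error. This stands as a defence of error control. It does not give the pairwise step 90% power.

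**The gap of 0.25 SD is not a declared target for any pair, and no configuration is assigned to it.** This also stands. A reader might infer that the comparison with clinician placement has 44% power as a matter of fact; that rests on an assumed mapping. If that gap were the 0.5 SD one, its power would be 95% and the shortfall would fall on the comparison with no mitigation.

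**The sample size is reviewed after each pilot** (sections 4 and 10.10). It is, but the review concerns variance and whether the sample reaches the power needed. It does not change the hypothesis being powered.

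**Covariate adjustment could raise power.** It could; the protocol quantifies no gain.

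**Two further inferences go too far.**

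- Stage 3 power cannot be computed by putting 12 bays into these formulas. Section 10.4 says the correlations needed are not available, and a bay is not a clinician.
- Dropout is not a material flaw. The protocol says "We expect a dropout rate of around 5" per cent, and 54 × 0.95 is about 51, where omnibus power is 89.3% against 91.1% at 54. Section 10.8 has inadequate sessions repeated, and section 10.10 plans imputation.

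**Conclusion.** The point holds in a limited form. The sample size calculation is correct for the test it names, but that test is not the primary objective, and the unqualified 90% in section 10.8 does not hold for both comparisons in that objective. On the plan's inputs, power at 54 clinicians is about 95% for a 0.5 SD contrast and about 44% for a 0.25 SD contrast, and at least one AISaT contrast is of the smaller size under any assignment of the means.

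This rests on the section 10.3 inputs (SD 1, correlation 0.5, equally spaced means), unadjusted two-sided 5% tests and no gain from covariates. That the weaker contrast is the one with clinician placement requires the further assumption that AISaT and no mitigation are the extremes. The conclusion concerns Stages 1 and 2 only.

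**What to change.** Amend sections 10.3 and 10.8 as follows.

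1. State that 90% is the power of the omnibus F-test, for Stages 1 and 2 only.
2. State which configuration carries which planning mean.
3. Give power for each AISaT contrast at 54 clinicians, two-sided 5%: about 95% at 0.5 SD, about 44% at 0.25 SD, and 90% at about 0.45 SD. Omnibus power at 51 clinicians (89.3%) can be added as a note.
4. Base the conclusion on the two AISaT contrasts from the mixed model, with familywise error controlled, and not on the omnibus result alone. Fixed-order testing (against no mitigation, then against clinician placement) is one valid option and needs no split of alpha; an omnibus gate followed by pairwise tests is another.

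These are wording changes to the protocol, to be carried into the analysis plan. Randomisation, data collection and sample size stay as they are. The cost is a less favourable stated power for one contrast; in return, a null result on that contrast will not be over-read.

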10.4 Planned recruitment rate

Two hospitals are recruiting to this study. The crucial participants to recruit for the first pilot and trial stage 1 is 27 clinicians in each hospital who perform outpatient consultations or aerosol generating procedures (AGPs). Of these, 12 will take part in both the pilot and the stage 1 trial. UCLH has a clinical staff of many thousands and sees 1,800,000 out-patients each year. This equates to around 200,000 separate clinic sessions in multiple clinical areas and there are many dozens of clinical consulting and AGP rooms throughout the estate. The Lister Hospital also has over 2,000 clinical staff and sees 800,000 outpatients each year (around 90,000 separate clinic sessions) and also has multiple clinical areas available. The PI at each site will engage local clinical colleagues, managers and clinical directors to support the work and clinicians who are expected to be in clinic for 3 weeks consecutively will be targeted for recruitment. We expect a dropout rate of around 5% as clinicians must give a minimum of 6 weeks' notice to cancel a clinic, so it is expected that the vast majority of clinicians who agree to take part will attend the relevant clinic sessions.

Recruitment is anticipated to be 10 clinicians per month for stage 1 and its pilot. For stage 2 (and its pilot), 54 clinicians will again be needed. Some of these may be the same ones who participated in stage 1. Recruitment is again anticipated to be 10 clinicians per month. The PI at the Lister Hospital and the CI, who works at UCLH, are both active clinicians who work in outpatients and AGP rooms. This should make recruitment of their clinical colleagues relatively straightforward. The dropout rate is again around 5% as described above.

Of patients attending these clinics and AGP sessions, almost 100% will be eligible and all of these will be invited to take part in the studies (we will not recruit in paediatric, obstetric or psychiatric clinics). Recruitment of patients is therefore likely to be around 300 with approximately 150 accompanying persons per month in both trial stages 1 and 2. Patients will either accept and enrol in the trial, or will not. If they accept and enrol, we do not expect drop-outs. If there were to be, this should have no major impact on the trial endpoints as we will be able to control for this in the data analysis phase. For a 4-hour clinical session, we expect to have 3 hours of analysable data approximately.

For trial stage 3 and its pilot, a total of 12 patient bays is required, 6 at each hospital and each will participate for 3 days. There is no formal sample size calculation for stage 3, as it requires inputs that we do not possess at the moment, including the correlation between the measurements within a bay, as well as the correlation over time. The design is a cluster randomised cross-over control trial. Given that there are 6 possible sequences of the 3 configurations, we chose 12 bays so that there are 2 bays per sequence.

Decisions about wards will be driven by senior clinical management. In wards, if patients accept the study, they will be in the bay until they are discharged, so no drop out is expected. Recruitment of other hospital staff to join the implementation science elements of the study is expected to be around 8-10 per month across the two sites for the duration of the study.

Loss to follow up is not considered to be relevant as participation is only for a very short period of time.

10.5 Randomisation methods

In study stages 1 and 2, clinicians will be randomised using simple randomisation to the order of the three different interventions. In study stage 3, ward bays will be randomised using simple randomisation. Each clinician or ward bay acts as its own control. Randomisation will be implemented using random permuted blocks. [name], Head of Statistics at the Comprehensive Clinical Trials Unit at UCL, will be in charge of randomisation using standard CCTU approaches.

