workflows and pathways. Staff will have the opportunity to test the tool and reflect on their experiences through a series of “Think Aloud” interviews (a common approach used in the usability testing of technological innovations). The researchers will observe the members of staff as they use the tool and will use questions in a pre-established interview topic guide to engage staff members in verbalising their thoughts as they are using the tool. The researcher will also carry out observations as the member of staff uses the tool and will record these in the form of fieldnotes. The research team will rely on regular feedback loops to share emerging findings from the usability testing with the clinical trial implementation team, and with the engineering team to refine the tool. Successive iterations of the AISaT software will be presented to an existing patient advisory group and professional stakeholder panel, to explore perceptions of members, ensure that development in the next period aligns with patient needs and to optimise the user interface.

Randomised Controlled Trial (RCT) Stages

Each **RCT stage** will be run in a cross-over format with aerosol droplet generation determined by the outcomes of the pilot phase.

The first two RCT stages will involve hospital clinicians at each hospital running a weekly session in the same clinic or AGP rooms. Each clinician will be involved for 3 weeks. There will be different configurations each week to allow direct comparison. The AISaT will be turned on and air quality safety measures will be implemented (including the use of air filters, screens, fans etc.), turned off completely with no extra air quality safety measures or air quality safety measures given to the clinician to use and place as they choose. The weekly order of these 3 different configurations will be randomised. These 3 segments of the trial will each be conducted over 3 consecutive weeks.

Fifty four clinicians and their patients will be invited to join, equating to roughly 27 clinicians per hospital. All patients attending either their outpatient clinic appointment or their AGP will be invited to join. Educational material will be made available in multiple languages to encourage broad participation from patients.

As these are cross-over trials, each clinician will be their own control.

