7.2 Registration/Randomisation Procedures

Participant registration will be undertaken by the local site team. Following participant consent, appropriately trained and qualified research personnel will register participants and each participant will be added to a Trial Participant Enrolment Log.

Clinician participants will be randomised into one of the three settings per clinic and this will be undertaken centrally by the coordinating trial team using a random number generator. The team includes a statistician who works at the UCL CCTU and all procedures will be done in line with CCTU best practice.

Patient (and accompanying person) participants will not be randomised.

All patients and clinicians will be unblinded, however the trial statistician, who is a member of the UCL CCTU team, will be blinded so that statistical analysis will be performed in a blinded way. Unblinding will be done at the end of analysis for each trial stage.

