7.4 Intervention Procedures

Each participant will take part on the day(s) that they attend the clinical environment, e.g. the clinic, AGP room or ward. Following consenting, the initial demographics/baseline data questionnaire will be completed with the research team member. This should take only several minutes. The patient (and accompanying person where applicable) will enter the clinical consulting room, AGP room or ward (depending on stage of trial).

The consented clinician will already have been randomised to one of the three settings:

Configuration 1: The AIaT will be turned on and air quality safety measures will be implemented. These may include the use of air filters, fans, screens etc.

Configuration 2: AIaT will be turned off completely with no extra air quality safety measures

Configuration 3: Air quality safety measures will be offered to the clinician to use and place as they see fit. The daily order of these 3 different configurations will be randomised.

The room will be set up accordingly by the research team. There will be no additional requirements from the patient or clinician throughout the duration of the clinic appointment, as the researchers set up the room themselves.

Some participants will also consent to take part in the implementation work which will involve follow-up questionnaires, such as the NoMAD questionnaire which will be conducted online. A schedule of all trial assessments and procedures is set out in Appendix 1.

The implementation research team will conduct their scoping work (semi-structured interviews, ethnographic observations, stakeholder workshops, usability testing) in a pilot phase, followed by Process Evaluation work during the clinical trials phase (NoMAD questionnaire, ethnographic observations, semi-structured interviews) and cost-effectiveness evaluation.

For an overview, please see Figure 1 in section 4. *Trial Design*.

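### Section 10.5 names two incompatible randomisation methods, only one of which gives the sequence balance the design relies on, and the Stage 3 failed-day rule does not say whether the configuration is kept

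*Protocol*

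**What the plan says.** **Method (Protocol 10.5).** For Stages 1 and 2, "clinicians will be randomised using simple randomisation to the order of the three different interventions". For Stage 3, "In study stage 3, ward bays will be randomised using simple randomisation". The same paragraph then states: "Randomisation will be implemented using random permuted blocks".

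**Balance relied on.** Section 10.3 obtains 53 clinicians and raises this to 54 because there are six possible sequences. Section 10.4 says there is no formal sample size calculation for Stage 3 and gives one reason for its size: "we chose 12 bays so that there are 2 bays per sequence".

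**What is randomised.** Section 4 randomises order: "The weekly order of these 3 different configurations will be randomised". Section 7.2 says "Clinician participants will be randomised into one of the three settings per clinic", and section 7.4 says "The consented clinician will already have been randomised to one of the three settings", although 7.4 goes on to say that the order of the configurations is randomised.

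**Failed data collection (10.8).** A Stage 1 or 2 session with under 2 hours of data is withdrawn and repeated in full. For a Stage 3 day with under 6 hours, the protocol says instead that the day's "randomisation will need to be rerun".

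**The concern.** Simple randomisation draws each unit's sequence independently and lets group sizes fall by chance. Permuted blocks force the sizes to be equal each time a block fills. A statistician building the lists from section 10.5 cannot follow both instructions. If the simple option is taken, the only stated basis for 12 bays in Stage 3 is lost. With unequal sequence groups, configuration is no longer orthogonal to week or day, so adjusting for period costs precision.

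The failed-day rule matters because each bay is its own control. If a failed day may receive a newly drawn configuration, a bay can have one configuration twice and another never. Sections 7.2 and 7.4 add to the uncertainty: they are the operational sections, and they describe allocation to a single setting rather than to a sequence.

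**Working it through.** **1. The plan's own figure.** Inputs from 10.3: means 0, 0.25, 0.5; SD 1; correlation 0.5 with compound symmetry; alpha 0.05. Squared deviations of the means from 0.25 sum to 0.125. The noncentrality is λ = n × 0.125 / (1 − 0.5) = 0.25n, with 2 and 2(n − 1) degrees of freedom and a Geisser-Greenhouse epsilon of 1 under compound symmetry.

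| n | Power |
|---|---|
| 52 | 89.9% |
| 53 | 90.5% |
| 54 | 91.1% |

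The minimum is 53, so the stated figure reproduces. Nothing below changes it.

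**2. Exact balance under simple randomisation to six sequences.**
- 12 bays, 2 each: 12! / (2!⁶ × 6¹²) = 0.0034, or 0.34%.
- 54 clinicians, 9 each: 54! / (9!⁶ × 6⁵⁴) = 0.000097, or about 0.01%.

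**3. At least one empty sequence, 12 bays.** By inclusion-exclusion: 6(5/6)¹² − 15(4/6)¹² + 20(3/6)¹² − 15(2/6)¹² + 6(1/6)¹² = 0.562, or 56%. For 54 clinicians the same calculation gives 0.0003.

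**4. What imbalance costs.** Simple allocation was simulated 20,000 times for each size. The average variance of the three pairwise configuration contrasts, in a model with unit and period effects, was divided by its value in the balanced design.

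| Units | Mean ratio | Median | 95th percentile |
|---|---|---|---|
| 12 bays | 1.108 | 1.090 | 1.283 |
| 54 clinicians | 1.020 | 1.016 | 1.048 |

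As effective size, the mean loss leaves about 12 / 1.108 = 10.8 bays and 54 / 1.020 = 52.9 clinicians.

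**5. Failed Stage 3 day.** Assume the bay's other two days stand with two different configurations. If the failed day is redrawn freely and equally from all three, only one outcome is the missing configuration, so the chance of missing it is 2/3. There are 12 × 3 = 36 bay-days. The protocol gives no Stage 3 failure rate, so the rate q is an assumption, shown as a range. Expected failed days are 36q, expected wrongly configured days are 36q × 2/3, and the chance of at least one is 1 − (1 − 2q/3)³⁶.

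| Assumed q | Failed days | Wrongly configured days | Chance of at least one |
|---|---|---|---|
| 2% | 0.72 | 0.5 | 38% |
| 5% | 1.8 | 1.2 | 70% |
| 10% | 3.6 | 2.4 | 92% |

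If the failed day keeps its allocated configuration, or the draw is limited to the missing one, the wrongly configured count is zero at every rate.

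**The case against.** The best defence is that the intent can be recovered. Section 10.5 says permuted blocks are how randomisation is implemented, and this agrees with the balance sought in 10.3 and 10.4. Block size and similar detail can sit in a randomisation specification. Chance imbalance does not bias a randomised crossover, and the cost with 54 clinicians is small. All of that stands. It does not remove the conflict, because the protocol itself names the method and names it two ways.

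Several stronger readings are tempting, and the document does not support them:

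- **That the Stage 3 rule breaks the crossover.** The contrast with the Stage 1 and 2 rule in the same paragraph favours a new draw, but the words can also mean redoing that randomised day. The rule is ambiguous, not demonstrably wrong.
- **That Stage 3 will fail at the rate given for Stages 1 and 2.** The figure of under 5% in 10.8 concerns clinic sessions needing 2 hours of data, which is a different threshold in a different setting.
- **That an affected bay is lost altogether.** Section 10.10 makes complete-case analysis an initial step, followed by multiple imputation and full information maximum likelihood. The mixed model in 10.8 can also use a bay with two configurations.
- **That 7.2 describes independent weekly draws.** Sections 4, 10.3, 10.5 and 10.8 all describe a crossover with three conditions per clinician. The phrase is loose wording.
- **That 27 clinicians per hospital is an error because it is not a multiple of six.** The split is approximate and stratification by hospital is not promised. Unstratified, 54 is nine full blocks of six.

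**Conclusion.** The contradiction in 10.5 is established. It matters most in Stage 3, where balance is the sole stated reason for 12 bays: simple randomisation achieves that balance with probability 0.34% and inflates contrast variance by about 11% on average (95th percentile 28%). In Stages 1 and 2 the mean inflation is about 2%, and no bias or material power problem is shown. These inflation figures assume a model with unit and period effects.

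The failed-day rule is a second, conditional point. It does harm only if read as a free redraw, and then its size depends on an assumed failure rate: about 0.5 to 2.4 wrongly configured bay-days for rates of 2% to 10%.

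This is a should-fix, to be done before the randomisation lists are generated.

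**What to change.** 1. **Section 10.5:** delete both references to simple randomisation. State that each clinician (Stages 1 and 2) or bay (Stage 3) is allocated once to one of the six sequences, using permuted blocks that fill exactly to 54 and 12, for example blocks of six. In Stage 3, one block of six per hospital is available at no cost, since each hospital has six bays.
2. **Sections 7.2 and 7.4:** replace allocation to one setting with allocation to a full sequence.
3. **Section 10.8:** replace the Stage 3 rerun rule with a statement that the failed day is repeated under the configuration it was allocated, with the actual date or period recorded and the failed attempt logged.

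The cost is amendment wording and a list specification. No participants are added and the sample sizes do not change.
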